3.2.1 Randomization and drug dispensing irregularities

Randomization and drug-dispensing irregularities occur whenever:

1. A randomization is not in accordance with the protocol-defined randomization method, such as a) a patient is randomized based on an incorrect stratum, or b) a patient is randomized twice.

OR

A patient is dispensed an IMP kit not allocated by the protocol-defined randomization, such as a) a patient at any time in the study is dispensed a different treatment kit than as randomized (which may or may not contain the correct-as-randomized IMP), or
 b) a non-randomized patient is treated with IMP reserved for randomized patients.

Randomization and drug-dispensing irregularities will be monitored throughout the study and reviewed on an ongoing basis.

All randomization and drug-dispensing irregularities will be documented in the clinical study report. These irregularities will be summarized by treatment group on the randomized population. Non-randomized, treated patients will be described separately.

Randomization and drug-dispensing irregularities to be prospectively identified include but are not limited to:

Table 5 - Randomization and drug allocation irregularities

Kit dispensation without IVRS/IWRS transaction
Erroneous kit dispensation
Patient randomized twice
Stratification error
A kit allocated at Day 1 or any unscheduled replacement before the up-titration visit (it may be the Month 2 or the Month 4 visit) is administered to the patient after the up-titration visit ^a
A kit allocated at any visit or unscheduled replacement from the up-titration visit, is administered to the patient after the next scheduled reallocation visit ^a
a Only if dose received is different from the one expected as per IVRS/IWRS allocation

3.3 ANALYSIS POPULATIONS

Patients treated without or before being randomized will not be considered randomized and will not be included in any analysis populations. The safety experience and CV events of patients treated and not randomized will be reported separately.

Randomized population: includes all randomized patients as defined in Section 3.2.

For any patient randomized more than once, only the data associated with the first randomization will be used in any analysis population. The safety experience associated with any later randomization will be assessed separately.

3.3.1 Efficacy populations

3.3.1.1 Intent-to-treat population

The primary efficacy analysis population will be the intent-to-treat (ITT) population, consisting of all randomized patients. Patients in the ITT population will be analyzed according to the treatment group allocated by randomization.

3.3.2 Safety population

The Safety population considered for safety analyses will be the randomized patients who actually received at least 1 dose or part of a dose of the double-blind IMP injection. Patients will be analyzed according to the treatment actually received (ie, as-treated treatment group, placebo or alirocumab).

In addition:

- Randomized patients for whom it is unclear whether they took the study medication will be included in the safety population in the treatment group as randomized;
- For patients receiving double-blind IMP injection from more than one treatment group during the trial (cases reported as protocol deviation), the treatment group used for as-treated analysis will be the one to which the patient was treated with the highest number of injections; in case of the same number of injections of each treatment is received, the as-treated treatment group will be the as-randomized group.

3.3.3 Anti-alirocumab antibody population

The ADA analysis will be performed on all randomized and treated patients (safety population) with an available ADA sample at Day 1 (baseline) and at least 1 available ADA sample post first double-blind IMP injection.

3.4 STATISTICAL METHODS

3.4.1 Demographics and baseline characteristics

Parameters described in Section 3.1.1 will be summarized by treatment group and overall using descriptive statistics.

Continuous data will be summarized using the number of available data, mean, standard deviation (SD), median, minimum, and maximum for each treatment group. First quartile (Q1) and third quartile (Q3) will be also provided for baseline lipid parameters, HbA_{1c}, and hs-CRP. Categorical and ordinal data will be summarized using the number and percentage of patients in each treatment group.

Unless otherwise specified, parameters will be summarized on the randomized population analyzed in the treatment group to which they were randomized. Similar analyses will be done on the safety population and will be included in the appendices if the size of the safety population is different (>10%) from the size of the randomized population for any treatment group. In the randomized population, parameters will also be summarized within each region.

All reported patient's medical and surgical history will be presented by primary SOC and HLT. The tables will be sorted by SOC internationally agreed order and decreasing frequency of HLT based on the overall incidence across treatment groups. In addition all medical history of specific interest will be presented by treatment group.

The diagnosis of diabetes mellitus at baseline (see also Section 3.1.1 for definition), as well as the source of diagnosis will be summarized in the randomized and safety populations by treatment group and overall, using the following mutually exclusive categories:

- From medical history or pre-treatment adverse events
- From anti-diabetic medications regardless of laboratory data (if no medical history of diabetes)
- From laboratory data only (if no medical history of diabetes and no anti-diabetic medications)

No specific description of the safety parameters will be provided at baseline. If relevant, the baseline values will be described along with each safety analysis.

3.4.2 Prior, concomitant or post-treatment medications

The prior, concomitant, and post-treatment medications will be presented for the randomized population.

Medications will be summarized by treatment group according to the WHO-DD dictionary, considering the first digit of the anatomical therapeutic chemical (ATC) class (anatomical category) and the first 3 digits of the ATC class (therapeutic category). All ATC codes corresponding to a medication will be summarized, and patients will be counted once in each ATC category (anatomical or therapeutic) linked to the medication. Therefore patients may be counted in several categories for the same medication.

The table for prior medications will be sorted by decreasing frequency of ATC followed by all other therapeutic classes based on the overall incidence across treatment groups. In case of equal frequency regarding ATCs (anatomical or therapeutic categories), alphabetical order will be used.

The tables for concomitant and post-treatment medications will be sorted by decreasing frequency of ATC followed by all other therapeutic classes based on the incidence in the alirocumab group. In case of equal frequency regarding ATCs (anatomical or therapeutic categories), alphabetical order will be used. In addition all medications of specific interest will be presented by treatment group.

The number and percentage of patients that took any statin for at least 3 months prior to the index ACS event (as reported on the e-CRF page "Additional statin information") will be displayed by treatment group.

The background lipid modifying therapy regimen at randomization will be summarized using the following categories:

- High dose atorvastatin/rosuvastatin (defined as daily atorvastatin 40 to 80 mg, or rosuvastatin 20 to 40 mg)
- Low/moderate dose atorvastatin/rosuvastatin (defined as daily atorvastatin <40 mg, or rosuvastatin <20 mg)
- Statin other than atorvastatin or rosuvastatin, at any dose
- Only LMT other than statin
- No LMT

The reason for not being on high dose at randomization will be supplied in tables giving numbers and percentages by treatment group.

Details (ie, statin names, doses) for patients who had received at least 2 statins the day of randomization (if any) will be listed.

For atorvastatin and rosuvastatin, the dose (in mg) will be also displayed by treatment group.

- Atorvastatin daily dose in mg (10, 20, 40, 80, Other);
- Rosuvastatin daily dose in mg (5, 10, 20, 40, Other);

The LMT other than statins will be summarized by pre-specified categories, chemical class or therapeutic class, and standardized medication name.

In addition the number (%) of patients in the following background LMT categories at randomization will be displayed:

- Ezetimibe and high dose atorvastatin/rosuvastatin
- Ezetimibe and low/moderate dose atorvastatin/rosuvastatin
- Ezetimibe and statin other than atorvastatin or rosuvastatin
- Ezetimibe and other LMT other than statin
- Only ezetimibe

LMT (statins and other LMTs) used after randomization during the study will be summarized over time graphically by treatment group and LMTs intensity at randomization using the following mutually exclusive categories:

- High dose atorvastatin/rosuvastatin
- Low/moderate dose atorvastatin/rosuvastastin
- Statin other than atorvastatin or rosuvastatin
- Only LMT other than statin
- No LMT

The reason for first modification in statin regimen after randomization will be also described.

The use of ezetimibe after randomization during the study will be also summarized over time graphically by treatment group.

The number (%) of patients initiating ezetimibe after randomization will be also displayed according to background LMT status at randomization.

3.4.3 Extent of investigational medicinal product exposure and compliance

The extent of IMP exposure and compliance will be assessed and summarized by actual treatment received within the safety population.

Double-blind IMP kits contain the following:

- Placebo for the ones administered to patients randomized in the placebo group
- 75 or 150 mg of alirocumab

Placebo injections administered to patients randomized in the alirocumab following 2 consecutive LDL-C <15 mg/dL will not be considered as double-blind IMP injections in the statistical analyses.

3.4.3.1 Extent of investigational medicinal product exposure

The total exposure will be assessed by:

- Duration of IMP exposure in months defined as: (last dose of double-blind IMP injection date + 14 first dose of double-blind IMP injection date) / 30.4375, regardless of intermittent discontinuations (see Section 3.5.3 for calculation in case of missing or incomplete data). Non-integer values will be rounded to one decimal place;
- The total number of double-blind IMP injections by patient;

In addition the duration of the observation period in months will be analyzed. The duration of observation period is defined as: (last contact date – randomization date+1)/30.4375. Non-integer values will be rounded to one decimal place.

These parameters will be summarized descriptively as a quantitative variable (number, mean, SD, median, minimum, and maximum). In addition, the durations of treatment exposure and observation period will be presented according to the following categories: <2, ≥ 2 to <6, ≥ 6 to <12, ≥ 12 to <24, ≥ 24 to <36, ≥ 36 to <48, ≥ 48 to <60, ≥ 60 months. The total number of double-blind IMP injections by patient will be presented similarly using the following categories: <4, ≥ 4 to <13, ≥ 13 to <26, ≥ 26 to <39, ≥ 39 to <52, ≥ 52 to <65, ≥ 65 to <78, ≥ 78 to <104, ≥ 104 to <120, ≥ 120 .

Additionally, the cumulative exposure will be provided in patient years.

Titration

The following summaries will be provided in the alirocumab group:

- The number (%) of patients with an up-titration to 150 mg, overall and according to the time of up-titration (ie, Month 2 and Month 4)
- The number (%) of patients with an up-titration followed by a down-titration to 75 mg
- The number (%) of patients with a switch to placebo
- The number (%) of patients on 75 mg, 150 mg, placebo over time (intermittent discontinuations won't be taken into account)

Cumulative exposure in patient-year by dose level (75 mg, 150 mg, placebo) will be provided, not taking into account intermittent discontinuations.

3.4.3.2 Compliance

Compliance will be assessed using the injection frequency that will be defined for each patient as the average number of days between 2 injections, that is: (last dose date – first dose date) / (number of injections – 1).

Cases of overdose (ie, 2 or more injections from the double-blind treatment kit are administered in <7 calendar days) will be summarized by treatment group. More generally, dosing irregularities are defined in Section 3.2.1.

3.4.4 Analyses of efficacy endpoints

All efficacy analyses will be performed based on ITT approach that will include events occurring from randomization to the analysis cut-off date for interim analysis or CSED for the final analysis, even after the patient has discontinued the study treatment. Any CV endpoint events occurring after the cut-off date/CSED will not be included in the analyses, regardless of the adjudication status. These events, if any, will be reported in a listing separately.

3.4.4.1 Analysis of primary efficacy endpoint(s)

The analysis of the primary efficacy endpoint will be the comparison between the two treatments using a log-rank test stratified by region (North America, South America, Western Europe, Eastern Europe, Asian, Other). The randomization is stratified by country but since the number of events per individual country is expected to be low (about 50 countries), the analysis will be stratified according to a grouping of countries into regions.

This primary comparison will be the 1-sided test (at 0.0249 type 1 error for the final analysis) of the following hypotheses at the final analysis:

H₀: HR \geq 1 versus H₁: HR <1

The estimates of the HR and corresponding confidence interval (CI) at $(1-2\alpha)$ % level (α being the 1-sided significance level: α =0.0249 at final analysis, α =0.0001 at second interim analysis) will be provided using a Cox Proportional Hazard model stratified by region. The underlying assumption of proportional hazards for Cox model will be checked by visual inspection of Kaplan-Meier plots. If proportionality is not observed, sensitivity analyses will be performed. In particular, the results will be presented by yearly intervals: the number of events per 100 patient-years for each yearly interval will be provided for each treatment group as well as the ratio of the two event rates. In addition, between-treatment cumulative rate ratios based on the Kaplan-Meier estimates and the corresponding 95% CIs) will be provided at yearly interval.

The cumulative incidence rate over time (at 6 months and by year) together with appropriate interval will be estimated by treatment group using Kaplan-Meier estimates.

Reasons for censoring (including patient who died before the cut-off date/CSED for other reason than CHD, lost to follow-up) will be summarized. For patients censored before the cut-off date/CSED, time from last contact when information on efficacy endpoints has been retrieved to cut-off date will be summarized.

Interim analyses

Two interim analyses will be performed. See Section 4 for description of these analyses. The cut-off dates of final (ie, CSED) and interim analyses are expected to be:

- First interim analysis date (futility): when 807 patients have experienced at least 1 primary efficacy event (50% fraction information);
- Second interim analysis date (futility and overwhelming efficacy): when 1210 patients have experienced at least 1 primary efficacy event (75% fraction information);
- Final analysis date: when 1613 patients have experienced at least 1 primary efficacy event or 24 months after the last date of randomization ex-China, whichever comes last.

Sensitivity analyses

The following sensitivity analyses will be performed:

Primary efficacy endpoint as per investigator

A sensitivity analysis of the primary efficacy endpoint will be performed including any events up to the CSED with final diagnosis by the investigator confirming the event, whether or not confirmed by the CEC. The statistical methodology used will be the same as defined for the primary efficacy analysis.

Since Investigators are requested to report any UA regardless of whether the event fulfils the stricter protocol definition or not, a subset of the reported UA will be selected using information reported on the e-CRF on hospitalization forms, additional information reported on the UA form related to ECG findings, need for revascularization procedure, and/or the concomitance of elevation of cardiac biomarkers (see Appendix C for full details). Since the categorization of deaths as CHD death was not requested from the Investigator, CHD deaths as per Investigator will include all deaths with primary cause of death reported as "Acute myocardial infarction", "Sudden cardiac death", "Heart failure or cardiogenic shock" as per investigator. The category "Undetermined cause of death" as per Investigator will be also included in this endpoint.

The concordance rate between Investigator opinion and adjudication by the CEC will be provided for all CV events adjudicated, by CV event's type.

Primary endpoint analysis excluding undetermined causes of death and undetermined causes of stroke

The primary efficacy analysis will be also performed excluding deaths adjudicated as "undetermined causes of death" and strokes adjudicated as "undetermined causes of stroke" by the CEC.

Supportive analyses

The primary efficacy outcome will be analyzed on randomized and treated patients considering only events that occurred during the treatment period (ie, from the first double-blind IMP injections to the last double-blind IMP injections +21 days, or up to the date of the CSED, whichever comes first), using the same statistical methodology as for the primary efficacy analysis. If a patient does not have a primary endpoint during the treatment period, the patient will be right-censored at the date of last contact when information on efficacy endpoints (presence or absence) has been retrieved, or at the date of death, or at the CSED or at the date of last double-blind IMP injection +21 days, whichever comes first.

Analysis on all events (ie, including recurrent events after the primary efficacy endpoints) will be also performed. Risk ratios between treatments groups will be estimated by Andersen-Gill (4) mean intensity model and the robust sandwich estimate of Lin and Wei (5) for the covariance matrix. Cumulative mean function and 95% CI in each treatment group will be calculated using Nelson-Aalen estimate.

Subgroup analyses

The consistency of the treatment effect on primary efficacy outcome will be evaluated with respect to the following demographic/baseline characteristic and prognostic factors:

- Gender;
- Age group ($<65, \ge 65$);
- Race (Caucasian, Black, Asian/Oriental, and Other, as appropriate);
- Country (IVRS stratum, depending of the size of subgroups);

- Region (USA/Non-USA, and North America/South America/Eastern Europe/Western Europe/Asia/Rest of world);
- Time from ACS event to randomization (eg, ≤ 24 weeks, ≥ 24 weeks).

For each factor except the region, a Cox proportional hazard model will be used, including the treatment, the region, the factor, and the treatment-by-factor interaction terms as covariates. Within each selected factor, the treatment effect hazard ratio and its CI will be estimated from this Cox model. P-values of interaction will be also provided. Results will be plotted using forests plot. The treatment effect by region will be estimated using the similar, Cox proportional model with treatment, region, and treatment-by-region interaction as the covariates.

In addition, Kaplan-Meier curves and summary statistics showing number of patients, number (%) of primary efficacy outcome events, cumulative incidence of events at 6 months and by year, and appropriate CI may be provided for each treatment arm in previously selected subgroups defined above.

In addition, the effect of the time from ACS to randomization (in weeks) will be assessed using a Cox Proportional Hazard model including the time from ACS event (continuous) as a covariate, the treatment group and the interaction.

In addition, homogeneity of treatment effect in the following subgroups will be explored (providing sufficient number of events per subgroups):

- BMI ($<30, \ge 30 \text{ kg/m}^2$)
- Age (<65, ≥ 65 to <75, ≥ 75)
- Ethnicity (hispanic or latino/not hispanic nor latino)
- Statin treatment at randomization in three categories (high dose atorvastatin/rosuvastatin; any other statin [ie, low/moderate doses of atorvastatin/rosuvastatin, any dose of other statins]; no statin)
- Diabetes mellitus status at baseline (diabetes, pre-diabetes/ normoglyceamic)
- Diabetes mellitus status at baseline (diabetes, pre-diabetes, normoglyceamic)
- Baseline LDL-C ($< 80, \ge 80$ to $< 100, \ge 100 \text{ mg/dL}$)
- Index ACS event (STEMI, NSTEMI, UA)
- Prior stroke
- Baseline non-HDL-C (<110, \geq 110 to <130, \geq 130 mg/dL)
- Baseline Apo B (<75, ≥ 75 to <90, ≥ 90 mg/dL)
- Baseline Lp (a) (<50, ≥ 50 mg/dL)
- Baseline hs-CRP (<2, ≥ 2 mg/L)

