#### 9.1.1 Primary efficacy endpoint

The primary efficacy endpoint is the time from randomization to first occurrence of one of the following clinical events, as determined by the CEC:

- CHD death (including “undetermined causes of death” as per the CEC)
- Any non-fatal MI
- Fatal and non-fatal ischemic stroke (including “stroke not otherwise specified” as per the CEC)
- Unstable angina requiring hospitalization

If none of these events is observed at the time of the analysis cut-off date (final or interim, depending of the analysis, see [Section 11.4.2.1](#) for details), the patient will be censored at the date of last contact, at the date of death, or at the date of cut-off, whichever comes first.

Of note, suspected event according to the investigator but not confirmed by the CEC will not be part of the primary efficacy outcome; their description will be provided separately.

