1 OVERVIEW AND INVESTIGATIONAL PLAN

1.1 STUDY DESIGN AND RANDOMIZATION

This is a double-blind, randomized, placebo-controlled, balanced (1:1, alirocumab:placebo), parallel-group, multi-national, multicenter study.

Randomization takes place 4 weeks to 52 weeks after the index event and is stratified according to country.

Prior to randomization, eligible patients enter a run-in period of at least 2 weeks but no more than 16 weeks, during which they receive statin-intensive therapy defined as daily atorvastatin 40 or 80 mg, or rosuvastatin 20 or 40 mg. In case patients are unable to tolerate atorvastatin 40/80 mg or rosuvastatin 20/40 mg, they are allowed to receive the maximal tolerated dose of atorvastatin or rosuvastatin; or under some documented circumstances for statin-intolerant patients, receive other lipid lowering treatment other than a statin (eg, ezetimibe, or other non-statin lipid modifying therapy [LMT]), or no LMT at all.

Following this run-in period, only patients not reaching goal on their current LMT at the qualifying visit, ie, LDL-C \geq 70 mg/dL (\geq 1.81 mmol/L) or apolipoprotein B (Apo B) \geq 80 mg/dL (\geq 0.8 g/L) or non-HDL-C \geq 100 mg/dL (\geq 2.59 mmol/L), are randomized to either background therapy + alirocumab or background therapy + placebo. All patients randomized to alirocumab initially receive alirocumab 75 mg every 2 weeks (Q2W). After randomization, patients on alirocumab not reaching the target LDL-C level at Month 1 have their dose up-titrated to 150 mg Q2W at Month 2 in a blinded fashion (in case Month 1 LDL-C is not available or not valid for potential up-titration at Month 2, the next available LDL-C sample at Month 2 is used for potential up-titration at Month 4).

The double-blind treatment period will continue until 24 months after the closing of randomization for all countries except for China or until the target number of events (1613) is reached, whichever comes last (this date will be the Common Study End Date [CSED]). The corresponding estimated study duration is 64 months. All patients, even if they have achieved an endpoint, or have prematurely discontinued study treatment, will be asked to remain in the study until the CSED and to come back to the site as close as possible to the CSED (ie, CSED visit).

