1.3 DETERMINATION OF SAMPLE SIZE

The sample size calculations are based on the primary efficacy variable, with the following assumptions:

• Primary efficacy endpoint is the time from randomization to the date of first occurrence of one of the following clinical events, as determined by the CEC: CHD death, any non-fatal MI, fatal or non-fatal ischemic stroke, or unstable angina requiring hospitalization (with new high-risk electrocardiogram (ECG) findings and contemporary evidence of angiographically significant coronary disease). Based on PROVE-IT results (1) and considering adjustment based on the study design and endpoints definition, the following Kaplan-Meier probabilities of event in the placebo group have been assumed: 3.8% at 12 months, 6.4% at 24 months, 9.0% at 36 months, and 11.4% at 48 months. Probabilities of an event at other time points are estimated using a piece-wise exponential model. The primary efficacy endpoint will be analyzed on an intent-to-treat basis (all randomized

patients, including those who discontinue study medication are followed for any efficacy event until the CSED).

- Treatment hazard ratio of 0.85 (corresponding to a 15% hazard risk reduction for the test group relative to placebo), which is assumed to be constant over time;
- A log-rank test at an overall 1-sided 2.5% significance level with 90% power;
- Two interim analyses, according to a group sequential design, using for efficacy Gamma (-22) α-spending function, and for futility a Gamma (-5) β-spending function. Non-binding spending functions are used. See Section 4 for interim analysis details;
- One percent lost-to-follow-up prior to a primary efficacy endpoint at 24 months in both arms;
- Enrolment rate: sample size of 18 000 patients enrolled in 1400 sites (all sites were expected to be activated over a 12 months period). Table 1 below describes the expected enrolment rate per month; these assumptions were based on internal experience to enroll this patient population.

Month	1 to 3	4	5	6	7	8	9	10	11	12 to 40
No. patients per month	32	64	80	104	160	240	320	420	520	560
Cumulative no. patients	96	160	240	344	504	744	1064	1484	2004	2564 at M12, 18 000 at M40

Table 1 - Enrolment rate assumptions per month

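### Kaplan-Meier cumulative incidence with deaths outside the endpoint censored overstates primary-endpoint risk in each arm, by about 0.1 to 0.4 points on 11.4% at 48 months under assumed death rates

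*SAP*

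**What the plan says.** **Estimator.** SAP 3.4.4.1 states that the cumulative incidence at 6 months and by year "will be estimated by treatment group using Kaplan-Meier estimates". Protocol 11.4.2.1 plans the same.

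**Censoring.** Protocol 9.1.1 states that without an event "the patient will be censored at the date of last contact, at the date of death, or at the date of cut-off", whichever is earliest. SAP 3.1.3.1 has the same rule, with last contact tied to the last information on efficacy endpoints. SAP 3.4.4.1 will summarise the reasons for censoring, "including patient who died before the cut-off date/CSED for other reason than CHD".

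**Which deaths are censored.** SAP 3.1.3.1 counts undetermined deaths as CHD death, and counts fatal ischemic stroke, with strokes not otherwise specified, as events. The censored deaths are the remainder: non-cardiovascular deaths, fatal hemorrhagic strokes, and other cardiovascular deaths not classed as CHD death.

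**Carry-over.** SAP 3.4.4.2 applies the primary methodology to the secondary endpoints. SAP 3.1.3.2 keeps the same censoring rules, except for a separate censoring date for CHD death, CV death and all-cause death. In the text available, neither document mentions a competing-risks estimator.

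**The concern.** Kaplan-Meier assumes that a censored patient stays at risk and would go on to have events like those still observed. That is reasonable for a patient whose follow-up is cut short, but not for one who has died. With such deaths censored, one minus Kaplan-Meier describes a population in which they do not occur. It is not the proportion of randomized patients who have a primary event by a given time, which is what cumulative incidence means. Whenever the competing death rate is above zero, the Kaplan-Meier figure is too high in each arm.

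At stake are the absolute risks by arm that readers will take from the report. The same method reaches the secondary endpoints. For non-fatal MI, unstable angina, revascularization and heart-failure hospitalization, every death outside the endpoint competes, CHD death included, so more deaths are censored than for the primary endpoint.

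**Working it through.** **1. The plan's own figure.** SAP 1.3 gives "A log-rank test at an overall 1-sided 2.5% significance level with 90% power" and "Treatment hazard ratio of 0.85 (corresponding to a 15% hazard risk reduction for the test group relative to placebo". With 1:1 allocation (SAP 1.1), Schoenfeld's formula for a fixed design is

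4 × (1.960 + 1.282)² / (ln 0.85)² ≈ 1592 events.

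Adding looks at 50%, 75% and 100% of events, "using for efficacy Gamma (-22) α-spending function, and for futility a Gamma (-5) β-spending function" and non-binding futility gives 1613.1 by numerical integration. The stated 1613 reproduces. It depends on the hazard ratio, alpha, power and looks, and not on how cumulative incidence is displayed.

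**2. Hazards.** SAP 1.3 states placebo Kaplan-Meier probabilities of 3.8%, 6.4%, 9.0% and 11.4% at 12, 24, 36 and 48 months, with a piecewise exponential model. The hazard λ in each year is the difference of successive values of −ln(1 − F): 0.0387, 0.0274, 0.0282 and 0.0267 per year. For alirocumab, multiply by 0.85. One minus Kaplan-Meier at 48 months is then:

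- placebo: 11.40%
- alirocumab: 1 − 0.886^0.85 = 9.78%
- difference: 1.62 points (1.623)

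**3. Competing deaths.** Let μ be the yearly hazard of death outside the endpoint. The documents give no value, so a range is assumed. In each year the cumulative incidence grows by

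S × λ/(λ + μ) × (1 − e^−(λ+μ)),

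where S is the proportion alive and event-free at the start of the year. This is the quantity that Aalen-Johansen estimates. For μ = 0.01:

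- placebo: S = 1, 0.9524, 0.9175, 0.8831; increments 0.03781 + 0.02561 + 0.02536 + 0.02318 = 0.1120
- alirocumab: increments 0.03223 + 0.02194 + 0.02182 + 0.02002 = 0.0960

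**4. Results at 48 months, same μ in both arms.**

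| μ per 100 patient-years | Placebo | Alirocumab | Difference (points) | Ratio |
|---|---|---|---|---|
| 0 (Kaplan-Meier) | 11.40% | 9.78% | 1.62 | 0.8576 |
| 0.5 | 11.30% | 9.69% | 1.61 | 0.8576 |
| 1.0 | 11.20% | 9.60% | 1.59 | 0.8576 |
| 2.0 | 11.00% | 9.43% | 1.57 | 0.8575 |

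Kaplan-Meier exceeds the cumulative incidence by 0.10, 0.20 and 0.40 points in placebo (0.9%, 1.8% and 3.7% relative) and by 0.09, 0.18 and 0.35 points in alirocumab. It overstates the difference by about 0.01, 0.03 and 0.06 points.

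**5. Unequal competing deaths.** Hold placebo μ at 1.0 per 100 patient-years:

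| Alirocumab μ | Difference (points) | Against the Kaplan-Meier 1.623 |
|---|---|---|
| 0.85 | 1.569 | Kaplan-Meier overstates |
| 1.15 | 1.621 | nearly equal |
| 1.30 | 1.647 | Kaplan-Meier understates |

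The break-even ratio of competing death hazards is about 1.16. It is 1.163 to 1.166 for placebo rates from 0.5 to 1.5.

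**The case against.** The strongest reply is that little depends on this. The planned inference is the stratified log-rank test and the Cox hazard ratio, and neither changes. The plan defines no risk difference or number needed to treat for the clinical endpoints. Broad event definitions and the entry criteria (recent cancer, short life expectancy and persistent severe heart failure are excluded) shrink the pool of censored deaths. The estimator is openly named, censoring reasons are tabulated, and two main secondary endpoints cannot be affected: all-cause death, and its composite with non-fatal MI and non-fatal ischemic stroke. The design rates are themselves Kaplan-Meier probabilities, so Kaplan-Meier output is what lets observed rates be compared with assumed ones.

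All of this stands. It makes the point minor and argues for keeping the Kaplan-Meier curves. It does not make the per-arm figures correct.

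A reader might go further and infer that the plan exaggerates treatment benefit, or that the yearly cumulative rate ratios will look too favourable. The documents do not support either. The direction of bias in the difference depends on how competing deaths split between the arms, which is unknown. Under equal hazards the ratio is the same to three decimals, and SAP 3.4.4.1 plans those ratios only if hazards are not proportional. Nor is every non-CHD death censored, since fatal ischemic and unspecified strokes are events.

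**Conclusion.** The point holds as a matter of reporting. The planned estimator overstates the absolute risk of the primary endpoint in each arm whenever deaths outside the endpoint occur. At 48 months the excess in placebo is about 0.1 to 0.4 points on 11.4%. Any effect on the between-arm difference is a few hundredths of a point under equal competing hazards, and its sign is not fixed.

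The sizes rest on the plan's placebo rates, a constant hazard ratio of 0.85, and assumed competing death rates of 0.5 to 2.0 per 100 patient-years. The documents neither give nor rule out values in that range. The effect on the secondary endpoints was not sized. Nothing here calls into question the primary test, the Cox hazard ratio, the alpha or the 1613 events.

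**What to change.** In SAP 3.4.4.1 and 3.4.4.2, add Aalen-Johansen cumulative incidence with confidence intervals by arm, at 6 months and by year, with death outside the endpoint as the competing event. Do this for the primary endpoint and for every secondary endpoint that does not include all-cause death. Keep the Kaplan-Meier curves for comparison with the design assumptions, and label them as censoring deaths outside the endpoint. Leave the log-rank and Cox analyses as they are.

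The cost is a few lines of SAP text and a little more programming in standard software. All causes of death are already adjudicated (SAP 1.2.2), so no new data are needed. The downside is slightly smaller reported absolute risks and two sets of figures to explain.
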